5.6. Permitted dose adjustments and interruptions of study treatment

Dosing interruptions are permitted in the case of logistical reasons not related to study therapy, e.g., an unrelated event such as a COVID-19-related travel restriction or any other restriction or safety concern with the subject traveling to the study site. The reason for interruption should be documented in the patient's study record.

Once the restriction(s) leading to study drug interruption have been lifted and the Sponsor and Investigator agree that it is safe for the subject to resume study participation, the subject may be resumed on study therapy on a case-by-case basis upon discussion with the Sponsor. Subjects who received only 1 dose of study drug before interruption may either resume study drug with the second dose or may restart with the first dose of study drug if a sufficient amount of time has elapsed such that the expected PD effect has returned to baseline.

5.7. Study Completion and Post-study Treatment

Each subject will be required to complete the study in its entirety and thereafter no further study treatment will be made available to them.

Study completion is defined as when the last subject completes their EoS visit, and any repeat assessments associated with this visit have been documented and followed-up appropriately by the Investigator, or in the event of an early study termination decision, the date of that decision.

All subjects will be required to attend the EoS visit and have related assessments collected as per the Schedule of assessments (Table 9). All SAEs reported during this time period must be reported as described in Section 7.6.2. and the Safety Management Plan. Documentation of attempts to contact the subject should be recorded in the source documentation.

5.8. Discontinuation of Study Treatment

The Investigator may decide to suspend the s.c. administration of the study drug if symptoms or signs consistent with an injection site reaction or hypersensitivity reaction occur.

Subjects who decide they do not wish to participate in the study further should NOT be considered withdrawn from the study UNLESS they withdraw their consent (see Section 4.3, Withdraw of Informed Consent). Where possible, they should return for the EoS assessments indicated in the assessment table. If they fail to return for these assessments for unknown reasons, every effort (e.g. telephone, e-mail, letter) should be made to contact the subject/pre-designated contact as specified in Section 4.3 (Lost to follow-up). This contact should preferably be done according to the study visit schedule.

5.9. Study Termination

The study can be terminated by Anthos at any time for any reason. This may include reasons related to the benefit/ risk assessment of participating in the study, practical reasons (including slow enrollment), or for regulatory or medical reasons. Should this be necessary, subjects must be seen as soon as possible and treated as a prematurely withdrawn subject and followed until the aPTT has returned to baseline. The Investigator may be informed of additional procedures to be followed in order to ensure that adequate consideration is given to the protection of the subject's interests. The Investigator will be responsible for informing the Institutional Review Board (IRB) of the early termination of the trial.

5.10. Emergency breaking of assigned treatment code

Emergency unblinding must only be undertaken when it is essential to treat the subject safely and efficaciously, such as in the event of clinically significant bleeding events. Most often, knowledge of the possible treatment assignments is sufficient to treat a study subject who presents with an emergency condition. A complete set of emergency code break cards will be provided to the Investigator site(s) and a complete set will be available at Anthos and Covance. All code break cards must be retained until the end of the study and retained by the site as a source document. They must be stored in a secure place but be accessible to the Investigator 24 hours per day in case of emergency. The Investigator will receive a blinded code break card for each subject. In an emergency, the code break may be opened to determine the treatment. There is no known reversal agent for MAA868 (see [Section 6.2](#)).

The code break should not be opened for any reason other than an emergency. If the Investigator opened the code break, he/she must note the date, time, and reason for removing it and retain this information with the case report form documentation. The unblinded treatment code must not be recorded on the CRF. The Investigator must also immediately inform the study monitor that the code has been broken.

It is the Investigator's responsibility to ensure that there is a dependable procedure in place to allow access to the code break cards at any time in case of emergency. The Investigator will need to provide:

- Protocol number
- Study drug name (if available)
- Subject number.

In addition, the Investigator must provide oral and written information to inform the subject how to contact his/her backup in cases of emergency when he/she is unavailable to ensure that unblinding can be performed at any time.

6. CONCOMITANT THERAPIES

6.1. Concomitant therapy

The Investigator must instruct the subject to notify the study staff of any new medications (including nutritional supplements and herbal medications) that he/she takes after being enrolled into the study.

All prescription medications, OTC drugs and significant non-drug therapies (including physical therapy and blood transfusions) administered or taken within the timeframe defined in the entry criteria prior to the start of the study and during the study, must be recorded on the Concomitant medications/Significant non-drug therapies CRF.

Medication entries should be specific to trade name, the single dose and unit, the frequency and route of administration, the start and discontinuation date and the reason for therapy.

Each concomitant drug must be individually assessed against all exclusion criteria/prohibited medication. If in doubt, the Investigator should contact Covance before randomizing a subject or, if the subject is already enrolled, to determine if the subject should continue participation in the study.

During the study, in the event the Investigator elects to start the patient on chronic antithrombotic therapy, anticoagulation or antiplatelet therapy should not be started until the patient's aPTT has returned to baseline.

Reporting medication errors including misuse/abuse

Medication errors are unintentional errors in the prescribing, dispensing, administration or monitoring of a medicine while under the control of a healthcare professional, patient/subject or consumer (EMA definition).

Misuse refers to situations where the medicinal product is intentionally and inappropriately used not in accordance with the protocol.

Abuse corresponds to the persistent or sporadic, intentional excessive use of a medicinal product, which is accompanied by harmful physical or psychological effects.

All study treatment errors and uses outside of what is foreseen in the protocol will be collected in the Dose Administration Record CRF. Study treatment errors are only to be reported to Covance DSS department if the treatment error is associated with an SAE.

All instances of misuse or abuse must be documented in the AE CRF irrespective of the misuse/abuse being associated with an AE/SAE. In addition, all instances of misuse or abuse must be reported to the Covance DSS department. As such, instances of misuse or abuse are also to be reported using the SAE form/CRF. [Table 3](#) summarizes the reporting requirements.

Table 3: Summary of reporting requirements for medication errors

Treatment error type	Document in Dose Administration CRF	Document in AE CRF	Complete SAE form/CRF
Unintentional study treatment error	Yes	Only if associated with an AE	Only if associated with an SAE
Misuse/Abuse	Yes	Yes	Yes, even if not associated with a SAE

For more information on AE and SAE definition and reporting requirements, please see [Section 7.6.1](#) and [Section 7.6.2](#), respectively.

6.2. Study restrictions

Pregnancy and contraception

Women of child-bearing potential are not permitted to participate in this study, unless they agree to use highly effective methods of contraception during their time in the study.

During their time in the study, sexually active male subjects must agree to use highly effective methods of contraception and should not father a child or donate sperm in this period.

Prohibited treatment

Use of the following medications is not allowed during the course of the study from screening (Visit 1) through the EoS. Patients who are receiving such medication(s) will be excluded, or if ethically and clinically justified, the medication(s) should be gradually withdrawn at least seven days before the baseline visit:

- Use of chronic antiplatelet agents such as clopidogrel or ticagrelor is prohibited; however, use of low-dose aspirin (≤ 100 mg per day) is permitted.
- Use of chronic systemic anticoagulants such as warfarin, low molecular weight heparin or heparinoids, or direct oral anticoagulants such as apixaban or dabigatran. Patients may be started on chronic anticoagulation during the Washout/Follow-up period once their aPTT has returned to baseline, at the Investigator's discretion.
- Use of any therapeutic monoclonal antibody regardless of the indication during the study.

Dietary restrictions

- No alcohol for 48 hours before each clinic visit (from Screening through the EoS visit). During the study, alcohol consumption will be restricted to no more than 2 drinks/day for males and 1 drink/day for females.
- Patients should not make significant alterations in their diet (e.g., going on weight loss diet) while in the study.
- During the study, caffeinated beverages will be restricted to no more than 3 cups/day.

Other restrictions

No strenuous physical exercise or activities which have an increased risk of injury or falling should be undertaken until after the EoS visit.

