3. INVESTIGATION PLAN

3.1. Overall Study Design and Plan Description

This is a phase 2a, randomized, subject- and investigator-blinded, placebo-controlled, multiple ascending dose-ranging study to assess the PK/PD, safety, tolerability, and immunogenicity of MAA868 in patients with AF or flutter.

Patients will be enrolled in at least 2 and up to 3 cohorts of approximately 16 patients each for a total of up to 48 subjects (Figure 1A). Patients in cohort 1 will be randomized 3:1 to receive a 120 mg dose of MAA868 or placebo, respectively on Day 1 with two subsequent monthly injections. After approximately 10 of the patients in cohort 1 have been randomized, a safety review of emerging safety and PK data from cohort 1 will take place. Cohort 2 may be initiated after it is confirmed by the Sponsor’s Medical Monitor and the Covance Lead Project Physician that the cohort 1 dose was safe and well tolerated after at least half of the patients in cohort 1 have been randomized. Likewise, after approximately 10 of the patients in cohort 2 have received their second dose and have been followed for at least an additional 14 days, interim safety, tolerability, and other analyses will be evaluated by the Sponsor. Based on emerging data, the Sponsor may elect to:

[figure not shown]
- Enroll cohort 3 to evaluate a higher, lower, or a previously studied dose of MAA868
- Terminate the study

The study is comprised of 3 periods:

- (1) Screening period of up to 28 days
- (2) Treatment period with MAA868 administered s.c. monthly (or matching placebo) (randomized 3:1) for 90 days
- (3) Follow-up period up to end of study (Day 170).

Following the screening period of up to 28 days, all patients that meet the study eligibility criteria (Section 4.1 and Section 4.2) will have baseline efficacy and safety assessments performed on Day 1 and then randomized to active or placebo (Figure 1B).

Figure 1: Overall study design

The first dose of study drug will be administered at the study center on Day 1. The second and third doses of study drug will also be administered at the study center to patients on the Day 31 visit and Day 61 visit, respectively.

During the treatment period, patients will return to the study center on Day 11, Day 31, Day 41, Day 61, Day 71, and Day 91 for safety assessments such as vital signs, AE assessments, laboratory tests, PK, PD, thrombogenesis biomarkers, and other study assessments according to the assessment schedule shown in [Table 9](#).

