4. SELECTION OF STUDY POPULATION

4.1. Inclusion Criteria

1. Written informed consent must be obtained before any assessment is performed
2. Male and female patients ≥ 18 and < 85 years old with paroxysmal atrial fibrillation (PAF) or atrial flutter on 12 lead electrocardiography at Screening Or
3. Patients with a history of PAF or atrial flutter, as documented by (telemetry, 12 lead electrocardiography or ambulatory [e.g. Holter] monitor) and not due to a reversible condition (e.g. alcohol binge drinking) can be entered even if they do not have PAF at Screening. There is not time-limit for this.
4. Patients with a CHA2DS2-VASc risk score (tool as a predictor for estimating the risk of stroke in patients with AF; Lip et al 2010) of 0-1 for men and 1-2 for women and in whom, in the investigator's judgment, the use of an anticoagulant for stroke prevention is not indicated
5. Body weight between 50 and 130 kg inclusive

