4.2. Exclusion Criteria

1. Use of other investigational drugs at the time of enrollment, or within 5 half-lives of enrollment, or until the expected PD effect has returned to baseline, whichever is longer; or longer if required by local regulations.
2. History of stroke, transient ischemic attack or systemic embolism
3. History of major bleeding during treatment with an anticoagulant or antiplatelet therapy. (Patients who have had major bleeding on anticoagulants or antiplatelet therapy more than a year ago can be enrolled only if the bleeding was due to a reversible cause, e.g. gastro-duodenal ulcer that was successfully treated.)
4. History of traumatic or non-traumatic intracranial, intraspinal or intraocular bleeding
5. Known bleeding diathesis or any known active bleeding site at screening or baseline
6. Family history of bleeding disorder
7. Known active GI lesions predisposing to bleeding events
8. Myocardial infarction, unstable angina pectoris or coronary artery bypass graft (CABG) surgery within 12 months prior to the Screening period
9. Known clinically significant valvular heart disease including moderate or severe mitral stenosis (valve area < 1.5 cm²).
10. Patients with a prosthetic heart valve
11. Uncontrolled hypertension defined as SBP/DBP $\geq 160/100$ mmHg at the Screening visit
12. Patients with NYHA Class III- IV heart failure
13. Currently being treated with anticoagulant therapy or have been on anticoagulants in the previous 12 months. Potential patients who have been on anticoagulation more than 12 months ago requires discussion with the sponsor before enrolling.
14. Treatment with antiplatelet therapy such as either a P2Y12 inhibitor or aspirin. (Low dose aspirin ≤ 100 mg/d) is allowed.)
15. Severe renal impairment as defined as an estimated glomerular filtration rate ≤ 45 mL/min/1.73m² by the MDRD equation at the Screening Visit

16. Positive test for human immunodeficiency virus (HIV), positive hepatitis B (hepatitis B surface antigen [HBsAg]) or hepatitis C (anti-hepatitis C antibody [Anti-HCV]) at Screening
17. Significant illness, per Investigator judgement, which has not resolved within four (4) weeks prior to dosing
18. Women of child-bearing potential, defined as all women physiologically capable of becoming pregnant, unless they are using highly effective methods of contraception during their time in the study. Highly effective contraception methods include:

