4.3. Discontinuation Criteria

Screen Failures

Screen failures are defined as patients who consent to participate in the clinical study but are not subsequently randomized. A minimal set of screen failure information is required to ensure transparent reporting of screen failure patients to meet the Consolidated Standards of Reporting Trials (CONSORT) publishing requirements and to respond to queries from regulatory authorities. Minimal information includes demography, screen failure details, eligibility criteria, and any serious adverse events (SAEs).

Patients who do not meet the criteria for participation in this study may be rescreened; however, each case must be discussed and agreed with the Sponsor on a case-by-case basis.

Withdrawal of informed consent

Subjects may voluntarily withdraw from the study for any reason at any time.

Withdrawal from the study can occur when a subject chooses to do one or more of the following:

- Does not want to participate in the study anymore
- Does not want any further visits or assessments
- Does not want any further study-related contacts
- Does not allow analysis of already obtained biologic material.

If a subject who has received one or more doses of the study drug determines that they no longer want to participate the Investigator must make every effort (e.g. telephone, e-mail, letter) to determine the primary reason(s) for the subject's decision to withdraw his/her consent, record this information and conduct any assessments and visits still allowed.

In the event the subject withdraws consent prior to beginning dosing, the study treatment will not be administered. The data that would have been collected at subsequent visits will be considered missing. Further attempts to contact the subject are allowed when safety findings require follow-up.

Lost to Follow-up

For subjects whose status is unclear because they fail to appear for study visits without stating an intention to discontinue or withdraw, the Investigator should show "due diligence" by documenting in the source documents steps taken to contact the subject, e.g. dates of telephone calls, registered letters, etc. A subject cannot be formally considered lost to follow-up until his/her scheduled end of study visit would have occurred.

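### Protocol 6.2 lets current anticoagulant users be withdrawn a week before baseline instead of excluded, but exclusion 13 bars any use in the previous 12 months, so withdrawal during screening cannot make them eligible

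*Protocol*

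**What the plan says.** The prohibited-treatment part of Protocol section 6.2 opens with a single rule for three drug classes: chronic antiplatelet agents, chronic anticoagulants and therapeutic monoclonal antibodies. Patients receiving any of them "will be excluded, or if ethically and clinically justified, the medication(s) should be gradually withdrawn at least seven days before the baseline visit". The second bullet reads "Use of chronic systemic anticoagulants such as warfarin, low molecular weight heparin or heparinoids, or direct oral anticoagulants such as apixaban or dabigatran". It makes no exception to the lead-in and does not refer to the exclusion criteria.

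Exclusion 13 in section 4.2, repeated in the synopsis, rules out patients who meet this description: "Currently being treated with anticoagulant therapy or have been on anticoagulants in the previous 12 months". For older use it adds: "Potential patients who have been on anticoagulation more than 12 months ago requires discussion with the sponsor before enrolling".

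Section 3.1 gives a "Screening period of up to 28 days", and Table 9 in Appendix 4 places it from Day -28 to Day -3. Sections 4.3 and 7.3 allow rescreening, case by case, with the sponsor's agreement. All of this is in the current protocol, Amendment 2.

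**The concern.** Sections 6.2 and 4.2 give different answers for the same patient. The 6.2 alternative is addressed to people who are taking the drug. For an anticoagulant, such a person fails the current-use limb of exclusion 13 before withdrawal and the 12-month limb after it. Section 6.2 nevertheless presents withdrawal as an alternative to exclusion, subject only to an ethical and clinical justification.

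The main stake is the patient's treatment. A site that followed 6.2 could stop an AF patient's anticoagulant in order to screen someone who cannot pass. Enrolment in breach of exclusion 13 is a second possibility, but an unlikely one.

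The conflict is confined to anticoagulants. Exclusion 14, on antiplatelet therapy, has no look-back period, so withdrawing an antiplatelet drug before baseline does not contradict it. No conflict is claimed for monoclonal antibodies.

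**Working it through.** The plan states no figure on this point, so there is none to reproduce. The check compares the drug-free time that 6.2 can produce with the time that exclusion 13 requires.

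**Inputs**
- Minimum drug-free time before baseline: 7 days (Protocol 6.2).
- Earliest screening day: Day -28 (Protocol Table 9; section 3.1 gives the same 28-day limit).
- Day numbering: no Day 0, since the day before Day 1 is Day -1 (SAP 6.1). Day -28 to Day 1 is therefore 28 days.
- Look-back: 12 months (exclusion 13), taken as 365 days.

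**Formula:** shortfall at Day 1 = look-back minus days off drug at Day 1.

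| Drug stopped | Days off drug at Day 1 | Share of look-back | Shortfall |
|---|---|---|---|
| Day -28 (longest possible) | 28 | 28/365 = 7.7% | 365 - 28 = 337 days |
| 7 days before baseline (6.2 minimum) | 7 | 7/365 = 1.9% | 365 - 7 = 358 days |

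Counting 12 months as 360 to 366 days changes the shortfalls only to 332 to 338 and 353 to 359 days. Tapering, which 6.2 calls for, can only reduce the drug-free time within screening. No stopping date inside one screening period comes near the requirement.

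**Rescreening.** If the look-back is judged at Day 1, that day would have to fall 337 to 358 days later, in a new screening. Exclusion 13 names no reference date, and Table 9 has eligibility checked at Screening as well as on Day 1. If the look-back must also be met at the new Screening visit, which is at the latest Day -3 and so 3 days before Day 1, Day 1 falls at least 365 + 3 = 368 days after stopping. The delay is then 368 - 28 = 340 to 368 - 7 = 361 days. The figures of 337 to 358 are thus a lower bound. On either reading, the patient would qualify because exclusion 13 had been satisfied, after the required sponsor discussion; the seven-day option would have contributed nothing.

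**The case against.** The strongest reply is that nothing in 6.2 declares a withdrawn patient eligible. It is a generic lead-in, and both sections can be obeyed by always choosing exclusion for anticoagulant users. Withdrawal is then necessary but not sufficient, and the defect is only a missing cross-reference. That reading is available, but it concedes that the withdrawal branch is never valid for this class within one screening period, although the text offers it.

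The second reply is that the protocol already guards against the error, and this largely stands:
- Section 3.1 makes meeting 4.1 and 4.2 a condition of randomization.
- Table 9 has the criteria checked at Screening and again on Day 1.
- Section 6.1 requires each drug to be checked against the exclusion criteria as well as the prohibited list, with a call to the CRO if in doubt.
- Exclusion 13 brings in the sponsor even for use more than 12 months ago.

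These provisions should prevent randomization. They do not necessarily act before a site has stopped the drug.

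The third reply is that few patients could be affected. Inclusion 4 requires the investigator to judge that "the use of an anticoagulant for stroke prevention is not indicated", and section 1.3 says the same in its benefit-risk discussion. A patient who needs the drug should not be withdrawn for this trial. That narrows the group but does not empty it. Section 1.3 describes the guidelines as equivocal at the CHA2DS2-VASc scores being recruited, so an investigator could judge that a low-score patient already on a DOAC does not need it. Such a patient would satisfy inclusion 4, withdrawal could look justified, and exclusion 13 would be the remaining bar.

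**Conclusion.** The concern holds as an internal inconsistency between Protocol 6.2 and exclusion 13, limited to anticoagulants and to a single screening period. That conclusion does not depend on how 12 months is counted or on the date at which the look-back is judged.

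Its practical weight is low. The documents give no basis for estimating how many patients are affected, enrolment of an ineligible patient by this route is unlikely, and neither sample size nor analysis changes. What remains is conflicting guidance that could lead a site to stop a patient's anticoagulant to no purpose. It is worth correcting but not urgent.

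**What to change.** Make two wording edits in Protocol 6.2:
1. In the lead-in, restrict the withdrawal option to the non-anticoagulant classes.
2. In the anticoagulant bullet, state that current use or use within the past 12 months is exclusionary under criterion 13, so stopping during screening does not make a patient eligible.

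Sections 4.1 and 4.2 stay as they are, and the SAP needs no change. Under section 10.1 the edits need a written amendment with sponsor and IRB approval, and health authority approval where required. They can be carried in the next amendment rather than prompting one.
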